HUMAN OR ANIMAL MATERIAL TRANSPORTED FOR RESEARCH, DIAGNOSIS, DISEASE TREATMENT, ETC.

PATIENT SPECIMENS FOR WHICH THERE IS MINIMAL LIKELIHOOD THAT PATHOGENS ARE PRESENT AND ARE TRANSPORTED IN A PACKAGING WHICH

CONFIDENTIAL

WILL PREVENT ANY LEAKAGE ARE CONSIDERED “EXEMPT HUMAN SPECIMEN” OR “EXEMPT ANIMAL SPECIMEN”.

THEY MUST BE LABELED AS “EXEMPT HUMAN/ANIMAL SPECIMEN”.
THEY MUST USE TRIPLE PACKAGING SYSTEM.

Processing of samples in Urobiologics laboratory:

Urine samples are processed to remove non-hormonal redox compounds and then reacted with a redox indicator to evaluate each sample in the pair of urines as an oxidative or a reductive reaction.

Results are reported to the UM C.L.A.S.S. Laboratory according to the randomized numbers provided with the samples.

At the conclusion of the study the residual de-identified urine will be shipped to the Sponsor. Upon completion of processing, the sponsor will destroy all remaining materials and verify the destruction and disposition to the class laboratory.

Statistical power analysis and planned stat analysis:

From each experimental subject, we will have three non-overlapping pairs of consecutive urine samples taken. For each sample pair a blinded determination will be made by Urobiologics as to which sample in the pair was reductive. For the sake of simplicity, consider the case where these samples are collected in 6 consecutive months. Let “A” be the event that the reductive sample in the pair corresponds to the earlier cycle and “B” its converse. Then, the hypothesis of alternating reductive cycles is supported if the sequences AAA or BBB are over-represented relative to others. To analyze this, we will map whether the 2nd and 3rd pairs are successfully determined conditional

CONFIDENTIAL

on the first. Let “Y” denote success and “N” denote failure. Each subject then has one of the four patterns: YY, YN, NY, NN representing whether the 2nd and 3rd paired cycles are correctly predicted by the alternating cycle hypothesis. The hypothesis is supported by over-representation of YY relative to chance if predictions were made under the null of $P(Y) = 0.5$ with successive pairs called independently.

Consequently, we will first use a chi-squared goodness of fit test to evaluate the hypothesis below at the $\alpha=0.01$ level:

$H_0: p = 0.5$

and $P(YY) = p*p$; $P(YN) = P(NY) = p*(1-p)$; $P(NN) = (1-p)*(1-p)$.

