Under the alternative that $p = 0.75$, 37 subjects are needed to give 90% power to reject the null hypothesis at a significance level of 0.01. Assuming that <10% of enrolled subjects will be lost to attrition, we need to enroll a minimum of 40 subjects to achieve the target sample size.

Subsequently, we will estimate “p” in the model above using the total proportion of “Y” and form a confidence interval for this estimate using a bootstrap procedure to account for the pairing of samples within women. As a secondary analysis, we will use a likelihood ratio test to evaluate the validity of the independence assumption by comparing the one-parameter independence model to the four-parameter model with unique cell probabilities. Finally, for exploratory analyses to generate future hypotheses we will fit a mixed logistic regression in which the log odds of outcome “Y” are expressed as a linear function of any covariates to be explored and a random intercept inducing correlation between repeated measures within each woman.

Study Flow Chart

Study Procedure	Screening	Cycle 1	Cycle 2	Cycle 3	Cycle 4	Cycle 5	Cycle 6	All samples processed
Informed Consent	X							
Inclusion/Exclusion form	X							
Medical History/ Demographics	X							
Assign a Subject Number	X							

Give three urine collection kits to subject.
 
Each kit will contain two units. The two units provide for two collections about a month apart for each kit. Each unit will have one cup, one green-cap vial, one dropper, one instruction sheet, and one form to fill out with period start date and dates of collection of sample along with other relevant queries and instructions for returning the samples.
 
When the subject believes THAT she will likely ship her specimens back and not return samples in person, THE STUDY WILL PROVIDE THE APPROPRIATE MATERIALS TO SHIP THE SPECIMEN THAT COMPLY WITH ALL D.O.T. REGULATIONS. THE STUDY WILL PROVIDE THE TRIPLE PACKAGING (1- VIAL, 2 SEALED BAG, 3- ENVELOPE) RETURN ENVELOPES WITH PREPAID RETURN SHIPPING LABEL. THESE URINE SAMPLES ARE CONSIDERED INFECTIOUS SUBSTANCES CATEGORY B (SEE NOTE BELOW), THEREFORE TO COMPLY WITH D.O.T. REGULATIONS THE SAMPLE MUST CONTAIN THE TEXT: "EXEMPT HUMAN SPECIMEN" WHICH MUST BE VISIBLE ON OUTSIDE OF ENVELOPE. THIS EXEMPT STATUS IS FOR SPECIMEN SHIPPING ONLY AND DOES NOT IMPLY ANY IRB EXEMPTION.
	X*							
Determine if subject accepts reminders	X							

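### The secondary likelihood ratio test miscounts the saturated model's parameters (three, not four, so 2 df) and tests equal success rates as well as independence

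*Combined protocol and SAP*

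**What the plan says.** The section Statistical power analysis and planned stat analysis scores the 2nd and 3rd cycle pairs as Y or N against the call on the first pair. It then says "Each subject then has one of the four patterns: YY, YN, NY, NN". The model has a single success probability p for both pairs: P(YY) = p², P(YN) = P(NY) = p(1 − p), P(NN) = (1 − p)². The primary analysis fixes p at 0.5 in that model and uses a chi-squared goodness-of-fit test at the 0.01 level.

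As a secondary analysis, the plan states: "we will use a likelihood ratio test to evaluate the validity of the independence assumption". The method is given as "comparing the one-parameter independence model to the four-parameter model with unique cell probabilities". It gives no degrees of freedom, significance level or reference distribution for this test.

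**The concern.** There are two separate points.

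- **Parameter count.** Four probabilities that must sum to 1 contain three free parameters. The degrees of freedom of a likelihood ratio test are the difference in free parameters, and the two counts in this sentence are the only guide the plan gives. Taken literally, they lead to 3 df. The test would then be too conservative and would miss dependence more often than it should.
- **What is tested.** The plan says that the test evaluates independence. The one-parameter model assumes two things: that the 2nd and 3rd pairs are independent, and that they share one success rate. A rejection may come from either. If the rates differ, independent pairs could be reported as dependent.

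**Working it through.** **Inputs from the plan:** four exclusive patterns per woman; one common p; null value 0.5; alternative 0.75; 37 evaluable women; at least 40 enrolled; primary alpha 0.01.

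**Assumptions, not in the plan:** alpha of 5% or 1% for the likelihood ratio test; the dependent cells; the unequal success rates.

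**Step 1: the plan's own figure.** The plan says: "Under the alternative that $p = 0.75$, 37 subjects are needed to give 90% power to reject the null hypothesis at a significance level of 0.01". This belongs to the primary test, whose null is fully specified, so 3 df is right there (3 − 0). At p = 0.75 the cells are 0.5625, 0.1875, 0.1875 and 0.0625, against 0.25 each. The critical value is 11.345 and the required noncentrality is 19.25. The likelihood-ratio noncentrality is 0.5232 per woman, so n = 19.25 / 0.5232 = 36.8, or 37. The Pearson version (0.5625 per woman) gives 34.2, or 35. Exact power of the Pearson test at 37 is 0.910. The figure of 37 is adequate and is not affected by this point. It does not show which df is intended for the secondary test.

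**Step 2: degrees of freedom of the secondary test.**

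- Saturated model: 4 cells − 1 constraint = 3 free parameters.
- One-parameter model: 1.
- df = 3 − 1 = 2. The counts as written give 4 − 1 = 3.
- Split of the 2 df, where logL is the maximised log-likelihood: logL(saturated) − logL(one p) = [logL(saturated) − logL(two rates, independent)] + [logL(two rates, independent) − logL(one p)]. The first bracket is independence (3 − 2 = 1 df). The second is equal rates (2 − 1 = 1 df).

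**Step 3: check by enumeration.** All 9,880 possible tables for n = 37 were enumerated. For each, G² = 2[logL(saturated) − logL(one p)], with the estimate of p equal to (2·YY + YN + NY)/(2n). Under the plan's model the mean of G² is 2.07 at p = 0.5 and 2.17 at p = 0.75, which fits 2 df. Critical values for 2 and 3 df are 5.99 and 7.81 at 5%, and 9.21 and 11.34 at 1%.

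**Step 4: effect of the df choice, n = 37.**

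| Truth | Nominal level | 2 df | 3 df |
|---|---|---|---|
| Plan's model, p = 0.5 | 5% | 5.6% | 2.3% |
| Plan's model, p = 0.75 | 5% | 6.1% | 2.7% |
| Plan's model, p = 0.5 | 1% | 1.2% | 0.4% |
| Plan's model, p = 0.75 | 1% | 1.3% | 0.4% |
| Dependent cells 0.625, 0.125, 0.125, 0.125 | 5% | 37.6% | 24.5% |

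The dependent cells are an assumption, but the scoring rule can produce them, because both later pairs are judged against the same first pair. Suppose each pair's call is right with probability a, independently. Then P(Y) = a² + (1 − a)² = 1 − 2a(1 − a). Setting this to 0.75 gives a(1 − a) = 0.125, so a = 0.854. Then P(YY) = a³ + (1 − a)³ = 1 − 3 × 0.125 = 0.625, P(YN) = P(NY) = 0.75 − 0.625 = 0.125, and P(NN) = 0.125.

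**Step 5: effect of the joint null, independent calls, n = 37, nominal 5%.**

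| Assumed rates, pair 2 / pair 3 | 2-df test rejects | 1-df test of independence rejects |
|---|---|---|
| 0.75 / 0.75 | 6.1% | 6.7% |
| 0.76 / 0.74 | 6.4% | 6.7% |
| 0.78 / 0.72 | 8.9% | 6.8% |
| 0.80 / 0.70 | 14.4% | 6.9% |
| 0.85 / 0.65 | 43.1% | 7.3% |
| 0.90 / 0.60 | 80.6% | 7.1% |

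At the dependent cells of Step 4 the 1-df test has 49.2% power, against 37.6% for the 2-df test.

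**Step 6: if all 40 complete.** There are 12,341 tables. At nominal 5% and p = 0.75, size is 6.6% with 2 df and 2.6% with 3 df. Power at the dependent cells is 40.1% against 28.6%. The pattern is the same.

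**The case against.** The plan states no df, so nobody is shown to have used the wrong one. The label may simply mean four named cell probabilities. The likelihoods and the statistic are the same whatever the model is called, and an analyst or program that counts free parameters will arrive at 2. This stands: every 3-df figure above is conditional, and if the constraint is applied only the wording of the count is at fault.

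On the joint null, both models are named openly, so a reader can see that the whole one-parameter model is being tested. The plan sets no rule that a rejection will be reported as dependence. Nor does it suggest that the two pairs have different success rates. The large rejection rates need gaps of 20 to 30 percentage points; with a gap of 2 points the effect is negligible (6.4% against 6.1%). This limits the likely size. It does not remove the mismatch between what the test is said to evaluate and what it tests, which remains with the correct df.

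Finally, nothing else in the plan depends on the result. The interval for p uses a bootstrap that allows for pairing within women, and the exploratory mixed model has a random intercept. Even with 2 df the test is weak at the dependent cells used here. All of this stands and is why the point is minor.

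**Conclusion.** The concern holds, as a minor point. The saturated model has three free parameters, not four, and the test has 2 df. That follows from the plan's own definition of the patterns and needs no assumption. The test is also joint, covering independence and equal success rates, which likewise follows from the plan's model.

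The size of the consequence does rest on assumptions. If 3 df were used at 5%, the size would be roughly half the nominal level, and power at the dependent cells considered would fall by about 13 percentage points (37.6% − 24.5%). If success rates differ between the 2nd and 3rd pairs, the chance of a misleading rejection runs from negligible at a 2-point gap to 14% at 10 points and 43% at 20 points. The primary test, the sample size of 37, the estimate of p and its bootstrap interval are unaffected.

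**What to change.** Revise the sentence on the likelihood ratio test to:

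- describe the larger model as saturated, with three free cell probabilities;
- refer the statistic to chi-square with 2 df, and state the significance level;
- describe it as a joint test of independence and of equal success rates for the 2nd and 3rd pairs.

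If independence alone is the question, compare the saturated model instead with a two-parameter independence model that has a separate success rate for each pair, on 1 df. This is optional. It answers the question as the plan words it and has more power at the dependent cells examined here.

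The cost is one sentence in the analysis plan, with no change to data collection, sample size or the primary analysis.
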